### **14.7.1 Adaptive Sample Size Determination**

In this section, an incidence of any primary adverse events will be referred to as a failure for the primary safety endpoint. The methods described in Broglio et al. will be used for adaptive determination of the sample size.

At the time of each interim analysis, predictive probabilities of success for safety will be calculated once using the current sample size and another time using the maximum sample size allowed. A uniform prior distribution will be assumed for the safety rate at the first interim analysis, and the distribution will be updated with the observed data at each subsequent interim analysis. The number of failures for the primary safety endpoint in subjects with incomplete information will be assumed to follow a beta-binomial distribution. The predicted number of failures for the primary safety endpoint will be estimated from these beta-binomial

distributions. The observed and predicted number of failures will provide estimates for the anticipated study outcomes with the sample size at the time of the interim analysis and the maximum sample size allowed. The Bayesian predictive probability of success for safety for each case will be calculated from these estimates.

Enrollment will be stopped if the predictive probability of success for safety with the current sample size is greater than 90% or if the predictive probability of success for safety using the maximum sample size allowed is less than 6.5%. Otherwise, enrollment will continue until the 230th subject is recruited. The Statistical Analysis Plan contains details on the timing of the interim analysis and estimation of the predictive probability of success at the interim looks. Regardless of whether enrollment stops at one of the interim analyses or continues to a sample size of 230 subjects, the primary safety and efficacy analyses will be conducted after all subjects have completed their 3-month post-procedure evaluation.

#### **14.7.2 Power and Type-I Error Simulations**

Trial simulations were performed to estimate the Type-I error rate and the power for the success of the safety endpoint under a range of assumptions for the true safety rate and the assumed enrollment schedule. For accrual rates of 1.7, 3.4, 5.1, 8.5, 11.9, 17, 20.4, 23.8, 25.5, 25.5, 25.5, 25.5, 25.5, and 25.5 patients per month for months 1 to 15 respectively, and true safety rates of 0 to 9.0%, the power for showing success for the safety endpoint is estimated to be greater than or equal to 80.0%. For a safety rate of 9.5% this power decreases to approximately 73.0%. Based on the feasibility study results discussed in section 14.7, it is unlikely that the safety event rate is higher than 9.0%. The posterior probability of the safety rate being less than or equal to 9.0% is estimated to be 0.886. Therefore, we expect the study to be sufficiently powered for the primary safety endpoint. With a true effectiveness rate of 96.0% and a performance goal of 80.0%, a minimum of 80 patients will provide 99.9% power for meeting the primary effectiveness endpoint. As a result, the power estimates for the primary safety endpoint closely estimate the overall power of the study.

Since the primary analysis is performed at a 5.0% level Type-I error and the sample size is selected independent of the effectiveness endpoint, the Type-I error for the effectiveness hypothesis is controlled at 5.0%. To estimate the Type-I error for the primary safety endpoint, we considered the hypothetical scenario that the primary safety endpoint is on the decision boundary (i.e. equal to 15%). Based on 25,000 trial simulations, the estimated Type-I error for this scenario was 4.7%. As the primary safety rate moves away from the decision boundary under the null hypothesis, the Type-I error for the test decreases. Since our study success is defined as meeting both primary safety and effectiveness endpoints and because the Type-I error for each of these tests is controlled at 5.0%, the overall study Type-I error will be controlled at 5.0% (Please refer to the SAP for more details).

Based on the simulation results, we concluded that the study is adequately powered to meet the primary safety and effectiveness endpoints and that the Type-I error for the overall trial success is controlled at 5%.

## 14.8 Analyses to be Conducted

### 14.8.1 General Conventions

Standard descriptive summaries for continuous data include the number of observations with data, number of observations with missing data, mean, standard deviation, median, minimum, and maximum values. For categorical data, the count and percent will be provided. Percentages will be based on the number of subjects without missing data.

### 14.8.2 Disposition of Study Subjects

Subject disposition will be summarized for all enrolled subjects by summary tables, listings and flow diagrams.

### 14.8.3 Demographic and Baseline Characteristics

All demographic characteristics, procedural, and immediate post-operative details will be summarized overall in the safety and mITT populations. Descriptive statistics will also be presented for roll-in subjects.

### 14.8.4 Analysis for Primary Effectiveness Endpoint

The primary effectiveness endpoint will be evaluated using the exact test for a binomial proportion at a one-sided significance level of 5%. If the lower bound of the exact two-sided 90% confidence interval of the primary effectiveness endpoint rate is greater than the performance goal of 80%, the study will be considered to have demonstrated effectiveness.

### 14.8.5 Analysis for Primary Safety Endpoint

The primary safety endpoint will be evaluated using the exact test for a binomial proportion at a one-sided significance level of 5%. If the upper bound of the exact two-sided 90% confidence interval of the primary safety endpoint rate is less than the performance goal of 15%, the study will be considered to have demonstrated safety.

### 14.8.6 Analyses of Secondary and Additional Endpoints

Percentage (%) of subjects with freedom from documented symptomatic atrial fibrillation (AF), atrial tachycardia (AT), or atypical (left side) atrial flutter (AFL) episodes will be estimated in the mITT population at 180 and 365 days with the corresponding one-sided 95% exact binomial lower bound.

Descriptive statistics will be presented for the remaining secondary endpoints in the Safety and mITT Populations overall and by roll-in cases. The neurological assessment related endpoints will be analyzed in the NAE population. No formal statistical hypotheses and

inferential statistics will be formulated and performed for the remaining effectiveness and safety endpoints. Details of analyses methods for secondary and additional endpoints will be provided in SAP.

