## 14 Statistical Methodology

### 14.1 Analysis Population

#### 14.1.1 Main-Study

- **Modified Intent-To-Treat (mITT) Population:** The Modified Intent-To-Treat (mITT) population consists of enrolled subjects who meet eligibility criteria and have the study catheter inserted.
- **Safety Population (SP):** The Safety Population will consist of all enrolled subjects who have undergone insertion of the study catheter.
- **Per Protocol (PP) Population:** The PP population is a subset of the mITT population and will include subjects who comply with the following criteria:

- Are enrolled and meet all eligibility criteria
  - Have undergone RF ablation with the study catheter
  - Have been treated for the study-related arrhythmia
- **Neurological Assessment Evaluable (NAE) Population:** The NAE Population will include at least 40 subjects who are subset of the Per Protocol Population, consent and are eligible for the required neurological assessments, and have post-ablation MRI. Assessment of incidence of new lesions requires availability of pre-and post MRI. Assessment of incidence of new deficits requires availability of pre-and post-neurological evaluation. Enrollment in the NAE population may be terminated prior to achieving the target number of subjects if study enrollment ends early after a planned interim look.

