8 ANALYSIS SETS

8.1 Main Study

For the analysis of study endpoints, the analysis populations defined in the following will be used:

- **Modified Intent-To-Treat (mITT) Population:** The mITT population will consist of enrolled subjects who meet eligibility criteria and have undergone insertion of the study catheters.
- **Safety Population (SP):** The SP will consist of all enrolled subjects who have undergone insertion of the study catheters.
- **Per Protocol (PP) Population:** The PP population is a subset of the mITT population and will include subjects who comply with the following criteria:
 - are enrolled and meet all eligibility criteria
 - have undergone RF ablation with study catheters
 - are treated for the study-related arrhythmia

Neurological Assessment Evaluable (NAE) Population: The NAE Population will include at least 40 subjects who are subset of the Per Protocol Population, consent and are eligible for the required neurological assessments, and have post-ablation MRI. Assessment of incidence of new lesions requires availability of pre-and post MRI. The subjects without pre-MRI but no lesion on post-MRI will be included in the NAE population. Assessment of incidence of new deficits requires availability of pre-and post-neurological evaluation. Enrollment in the NAE population may be terminated prior to achieving the target number of subjects if study enrollment ends early after a planned interim look.

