11.5.2 Secondary Effectiveness Analysis

11.5.2.1 Secondary Effectiveness Endpoints of Effectiveness Success

Secondary effectiveness endpoints, including 6-Month Effectiveness Success and 12-Month Effectiveness Success will be summarized descriptively for all subjects in the PP population and roll-in subjects treating the endpoint as a binary variable. The point estimate and the one-sided 95% exact binomial lower bound will be presented. The secondary effectiveness analysis will

also be performed in the Safety Population for all enrolled subjects who had study catheter inserted and RF delivered with study catheters.

Time to Event Analysis:

Time to event analysis will also be performed for these secondary effectiveness endpoints. Kaplan-Meier curves and survival estimates will be provided using data on all subjects in the PP population and roll-in subjects. The subjects who do not have effectiveness failures but are followed up less than the endpoint-specified evaluation periods will be censored at their last observations.

Subgroup Analysis:

In order to provide additional characterization and interpretation of the outcomes of 6-Month and 12-Month effectiveness success, subgroup analyses based on AAD history at baseline will be performed in the PP population.

For AAD history, subjects will be categorized into AAD refractory and the AAD naïve subgroups. The AAD refractory subgroup will consist of subjects who at any point prior to their enrollment received a Class I, II, III or IV AAD for treating AF. The AAD naïve subgroup will include subjects who never received any Class I to IV AADs prior to their enrollment.

The number and percentage of subjects with the secondary effectiveness endpoints will be presented in each subgroup. Kaplan-Meier estimates will also be presented by AAD history at baseline.

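### SAP 11.5.2.1 plans no mITT analysis of 6- and 12-month arrhythmia freedom, although protocol 14.8.6 names the mITT, and neither document says how subjects with no RF delivered are classified

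*Protocol*

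**What the plan says.** Protocol 14.8.6 fixes the population for symptomatic freedom at both time points: it "will be estimated in the mITT population at 180 and 365 days", with a one-sided 95% exact binomial lower bound. Its next paragraph covers the other secondary endpoints, among them freedom from any documented recurrence: "Descriptive statistics will be presented for the remaining secondary endpoints in the Safety and mITT Populations overall and by roll-in cases".

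The mITT does not require energy delivery in either document. Protocol 14.1.1 defines it as "enrolled subjects who meet eligibility criteria and have the study catheter inserted", and SAP 8.1 as "enrolled subjects who meet eligibility criteria and have undergone insertion of the study catheters".

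SAP 11.5.2.1 keeps the exact lower bound but changes the population. The 6- and 12-month endpoints "will be summarized descriptively for all subjects in the PP population and roll-in subjects treating the endpoint as a binary variable". A further analysis will "also be performed in the Safety Population for all enrolled subjects who had study catheter inserted and RF delivered with study catheters". The Kaplan-Meier estimates use the PP population and roll-in subjects, and the subgroups by antiarrhythmic drug history use PP. PP members must, among other criteria, "have undergone RF ablation with study catheters" (SAP 8.1).

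Protocol 4.4 names the subjects at issue. Discontinued subjects are those with the study catheter inserted but no RF energy delivered, and they stay in follow-up for 30 days. SAP 11.5 states that all secondary endpoints are analysed without subjects whose outcome is missing.

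**The concern.** The protocol names a population for these endpoints, and the SAP plans no analysis in it and gives no reason. A reader who works from protocol 14.8.6 would look for a table that the SAP does not produce.

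The populations differ in a way that bears on effectiveness. Every set used in SAP 11.5.2.1 is conditional on RF having been delivered. The primary effectiveness analysis is also in PP (protocol 14.5.1, SAP 11.4.1), and its sensitivity analysis in SAP 11.4.5 is again limited to subjects with RF delivered. The mITT summaries in protocol 14.8.6 were thus the place where an effectiveness denominator could have included subjects in whom the catheter was inserted and no RF was delivered. In a single-arm study meant to support CE-mark registration, it matters whether the reported long-term rate describes all eligible subjects in whom the device was used or only those who were ablated.

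**Working it through.** The documents state no freedom rate or expected share of non-ablated subjects, so there is no figure to reproduce. The check is a comparison of populations, followed by an illustration.

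**Step 1: populations side by side**

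| Analysis of freedom | Population | RF required? |
|---|---|---|
| Protocol 14.8.6, symptomatic, 180 and 365 days | mITT | No |
| Protocol 14.8.6, any documented recurrence | Safety and mITT | No |
| SAP 11.5.2.1, binary rate | PP; roll-in | Yes (SAP 8.1, 8.2) |
| SAP 11.5.2.1, further analysis | Safety Population with RF delivered | Yes |
| SAP 11.5.2.1, Kaplan-Meier | PP; roll-in | Yes |
| SAP 11.5.2.1, drug-history subgroups | PP | Yes |

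None of the four SAP rows is in the mITT, and none can contain a subject without RF. The mITT does appear among the SAP's secondary analyses, but only for safety (SAP 11.5.1).

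**Step 2: would naming the mITT be enough?** The endpoint windows run from day 91 to day 180 and from day 91 to day 365. Discontinued subjects leave follow-up at day 30, so they have no outcome in either window. Under the missing-outcome rule in SAP 11.5 they would leave an mITT denominator as well. The population and the classification rule therefore have to be settled together.

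**Step 3: illustration.** Let N be the mITT size, d the number with no RF delivered, and x the number free of arrhythmia among the N − d treated. For simplicity, assume that all treated subjects are in PP and have an outcome.

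- RF-only rate: x/(N − d).
- mITT rate with the d subjects counted as non-success: x/N.
- Difference: [x/(N − d)] × d/N.
- One-sided 95% exact lower bound for x of n: the 5th percentile of Beta(x, n − x + 1).

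N = 230 is the maximum main-study size and N = 80 the first interim look. Freedom of about 70% and every value of d are assumptions.

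| N | d | RF-only rate (bound) | mITT rate (bound) | Difference, points |
|---|---|---|---|---|
| 230 | 0 | 161/230 = 70.0% (64.6%) | 161/230 = 70.0% (64.6%) | 0 |
| 230 | 2 | 160/228 = 70.2% (64.8%) | 160/230 = 69.6% (64.2%) | 0.6 |
| 230 | 5 | 158/225 = 70.2% (64.8%) | 158/230 = 68.7% (63.3%) | 1.5 |
| 230 | 10 | 154/220 = 70.0% (64.5%) | 154/230 = 67.0% (61.5%) | 3.0 |
| 80 | 2 | 55/78 = 70.5% (60.9%) | 55/80 = 68.8% (59.2%) | 1.8 |
| 80 | 5 | 52/75 = 69.3% (59.4%) | 52/80 = 65.0% (55.3%) | 4.3 |

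Check of the third row: 0.7022 × 5/230 = 0.0153.

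Over assumed freedom of 60% to 80%, the difference is about 0.3 to 3.5 points at N = 230 for d from 1 to 10, and about 0.7 to 5.0 points at N = 80 for d from 1 to 5. If the mITT is used but missing outcomes are still excluded, the denominator returns to N − d and the difference is zero.

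**The case against.** The strongest reply is that the change of population does not by itself remove anyone. Without follow-up after day 30, discontinued subjects have no outcome to analyse, and SAP 11.5 would drop them from an mITT rate too. This is correct. A reader might infer that the move from mITT to PP is what inflates the rate. The documents do not support that: any inflation depends on counting these subjects as non-success, a rule that protocol 14.8.6 does not contain.

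The number affected may also be very small. In the feasibility study (protocol 1.2.3), 39 of 40 enrolled subjects were treated, the other was excluded before the procedure, and no inserted-but-not-ablated case is described. Protocol 8.2.2.3 excludes subjects who need ablation outside the PV or CTI region before a study catheter goes in. This stands, and it is why the sizes above are illustrations and not estimates.

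A reader might also infer that the SAP ignores these subjects altogether. It does not. They appear in disposition (SAP 11.2), in the Safety Population analyses (SAP 11.4.5, 11.5.1) and, if eligible, in the mITT set for primary safety, subject to its follow-up rule (SAP 11.4.2). The gap is in effectiveness. Nor does protocol 4.4 say that the catheter could not be used in a discontinued subject; the definition covers no RF delivered for any reason.

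Finally, PP is the primary effectiveness set in both documents, and protocol 14.8.6 leaves details of method to the SAP. That makes a PP result reasonable to report. It does not explain omitting a population that the protocol had already named.

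**Conclusion.** The inconsistency holds. The protocol specifies the mITT for symptomatic freedom at 180 and 365 days, and the Safety and mITT populations for freedom from any documented recurrence. The SAP plans no mITT analysis of either, and each of its analyses is conditional on RF delivery. Beneath this lies a second gap: neither document says how an eligible subject with the catheter inserted and no RF delivered is to be classified.

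The size cannot be determined from the documents. It is zero if every inserted subject receives RF or if such subjects are dropped as missing. If they count as non-success, a handful of them would lower the rate and its bound by roughly one to two points at 230 subjects, and by more if enrollment stops near 80. Those figures rest on an assumed freedom rate, an assumed count and the added rule.

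The endpoints are secondary and descriptive. The primary safety and effectiveness tests, alpha and power do not depend on them.

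**What to change.** In SAP 11.5.2.1:

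- Add the mITT estimate of 6- and 12-month freedom that protocol 14.8.6 specifies, with its one-sided 95% exact lower bound, and include the any-documented-recurrence endpoints.
- State that, in this analysis, eligible subjects with the catheter inserted but no RF delivered count as non-success, as an exception to the missing-outcome exclusion in SAP 11.5. Record this as a rule added by the SAP, since protocol 14.8.6 does not state it.
- Report the PP result beside the mITT result, and give the number of subjects with no RF delivered so that the difference can be traced.

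The cost is one more table, a written classification rule, and possibly a slightly lower reported rate. No new data collection is needed.

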#### **14.8.7 Handling of Missing Data**

Patients with missing effectiveness data will be excluded from the primary effectiveness analysis. Sensitivity analyses for missing data will be performed in the PP populations to assess the impact of missing values on the primary effectiveness outcome and are described in the SAP. Subjects with missing primary safety data will also be excluded from the primary safety analysis. Sensitivity analyses for missing data will be performed in SP and mITT populations and are described in the Statistical Analysis Plan (SAP)

### **14.9 Interim Monitoring**

An independent statistician will be responsible for conducting the interim analyses and reviewing the results with a designated Data Monitoring Committee (DMC). The DMC charter will document the role and responsibilities of the committee and the independent statistician.

## **15 Ethics and Protection of Human Subjects**

### **15.1 Ethical Standard**

As the Sponsor of this study, Biosense Webster has the overall responsibility for the conduct of the study, including assurance that the study meets the regulatory requirements of the Food and Drug Administration and the MDD 93/42/EC and the local government. The Sponsor will also maintain compliance with Good Clinical Practice (ICH version 4 du 1 May 1996), the European standard EN ISO 14155:2011 (Clinical Investigation of Medical Devices for Human Subjects), the Declaration of Helsinki (Ethical Principles for Medical Research Involving Human Subjects, Tokyo 2004), Sponsor general duties (21 CFR 812.40), selection of investigators (21 CFR 812.43), monitoring (21 CFR 812.46), supplemental applications (21 CFR 812.35 [a] and [b]), maintaining records (21 CFR 812.140 [b]), and submitting reports (21 CFR 812.150 [b]), and to local regulations where required.

- **General Duties**  
Biosense Webster's general duties consist of submitting the clinical investigation application to appropriate regulatory agencies, assuring that sites have received EC approvals prior to shipping the devices, selecting investigators, ensuring proper clinical site monitoring and ensuring subject informed consent is obtained.
- **Data Quality and Reporting**  
Biosense Webster is responsible for providing quality data that satisfy federal regulations and informing proper authorities of serious unanticipated adverse events and deviations from the protocol.

- **Selection of Investigators**  
All potential investigational sites will undergo an evaluation to ensure that the site has the appropriate facilities and personnel to conduct the study in compliance with the clinical investigational plan. Based on outcome of evaluation process, Biosense Webster will select qualified investigators, ship devices only to participating investigators, obtain a signed Investigator's Agreement and provide the investigators with the information necessary to conduct the study.
- **Supplemental Applications**  
As appropriate, Biosense Webster will submit changes in the Clinical Investigational Plan to the investigators to obtain all applicable re-approvals.
- **Maintaining Records**  
Biosense Webster will maintain copies of correspondence, data, adverse device effects and other records related to the study. Biosense Webster will maintain records related to the signed Investigator Agreements.
- **Submitting Reports**  
Biosense Webster will submit any required regulatory reports identified in this section of the regulation. This may include unanticipated adverse device effects, withdrawal of EC approval, current investigators list, annual progress reports, recall information, final reports and protocol deviations.

